12.6.5 Ophthalmologic Examinations

Subjects will undergo an OE at the time points in Part A [Table 3-1](#), Part B [Table 3-2](#) and [Table 3-3](#), and Part A/B Cohort 8 [Table 16-1](#). The OE must be conducted by a licensed ophthalmologist, preferably a pediatric ophthalmologist. The OE will include:

- examination of the lens with a slit-lamp (portable or otherwise; pharmacologically-dilated examination). Details of the slit-lamp examination will be documented.
- assessment of the red reflex (pharmacologically-dilated examination)
- Screening OEs only: examination of the fundus (retina, optic nerve, and vessels), pupils, and eye movements

In addition, at screening, relevant medical history will be obtained for all subjects, including the following:

- history of steroid use
- history of trauma to the eye
- any family history of glaucoma, congenital cataracts, or cataracts arising later in life

At screening for all Parts, the subject is not eligible for enrollment if:

- an adequate slit-lamp examination cannot be conducted
- a lens opacity/cataract is identified (excluding those considered congenital and nonprogressive, such as a suture cataract)

During the screening period, if an adequate slit-lamp examination cannot be conducted, the slit-lamp examination may be repeated until an adequate repeat slit-lamp examination is completed (Sections 9.1.1.1 and 9.1.1.3) and eligibility criteria regarding the ophthalmologic findings are met.

For Part A, the Follow-up OE will be performed 8 weeks after the last dose of study drug (Section 9.1.3.1).

During the Part B and Part A/B Cohort 8 treatment periods, if a new lens opacity or cataract is identified at any OE, the Vertex medical monitor must be notified and study drug dosing must be discontinued. If an adequate slit-lamp examination cannot be conducted at any visit where it is required in Part B (Table 3-2) or Part A/B Cohort 8 (Table 16-1), the subject will continue receiving study drug until an adequate repeat examination is completed (within 4 weeks of the study visit). If an adequate slit-lamp examination cannot be conducted within 4 weeks of the study visit, study drug dosing may be discontinued.

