Vertex recommends that subjects and sites refer to local guidance regarding travel restrictions. There are no operational changes to the study protocols for subjects who can travel to the study sites for their visits. However, to ensure continued safety of subjects who *cannot* travel to the study sites for their visits (for any reason due to COVID-19), specific alternative measures are being implemented to minimize the risk of exposure to COVID-19 (see table below). As the COVID-19 pandemic evolves, Vertex will continue to assess the need for additional actions to ensure the safety of all involved in these clinical studies.

Addendum Version 3.0 summarizes additional measures taken for these ongoing CF clinical studies (see table below) to ensure continued safety.

Summary of Changes in Ongoing CF Clinical Studies for Subjects Who Cannot Travel to the Study Site

Protocol Change	Rationale for Change	Study Number
Addendum Version 3.0, dated 29 July 2020		

Assessments
 
Unscheduled visit(s) will be permissible at the discretion of the investigator(s) or Vertex. The unscheduled visit(s) may be conducted at any time during the study (including after the protocol defined last study visit) in the event assessments specified to be collected at a scheduled visit were not collected due to COVID-19.
	
To ensure subject safety and/or to facilitate evaluation of safety and/or efficacy if assessments are not performed per the schedule in the protocol due to COVID-19.
	
VX15-770-124
 
[REDACTED]
 
[REDACTED]
 
[REDACTED]
 
[REDACTED]
 
[REDACTED]

Implementaion of measures described in addenda versions 1.0 and 2.0, as applicable.
	
To ensure subject safety and/or to facilitate evaluation of safety and/or efficacy while maintaining study integrity and the safety of subjects and site personnel.
	
[REDACTED]

Summary of Changes in Ongoing CF Clinical Studies for Subjects Who Cannot Travel to the Study Site

Protocol Change	Rationale for Change	Study Number
Addendum Version 2.0, dated 15 May 2020		

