
Safety Assessments and Reporting
 
Safety assessments, as indicated per protocol, may be performed by qualified personnel conducting the in-home visits (e.g., personnel from site or qualified health care agency). These assessments may include the following, as indicated per protocol, and per local regulation:
 
 • vital signs • pulse oximetry • height/length/stature • weight • physical examination (complete or abbreviated) • pregnancy test (serum or urine) • urinalysis • blood draws for safety test panels (chemistry, LFT panel, lipid panel, hematology, coagulation). 
Blood and/or urine samples for safety assessments are analyzed as indicated per protocol for subjects who have in-home visits.
 
Blood and/or urine samples for safety assessments may be collected and analyzed at local laboratories for subjects who do not have in-home visits, but do not complete the assessment at the site.
 
In addition, safety assessments will be evaluated by telephone. These assessments may include the review of the following:
 
 • AEs • signs and symptoms/systems for CF • medications • planned or unplanned hospitalizations for CF • study drug administration • outcomes related to PEX • outcomes related to antibiotic treatment 
Investigators will review results (in-home and telephone) and contact subjects for follow-up as needed.
 
All data will continue to be retained in the subject’s source files.
 
Any clinically significant finding (e.g., AE, SAE, laboratory abnormalities) will continue to be reported as indicated per protocol.
	
To assess the safety and tolerability of the CFTR modulator evaluated in the specific clinical study while ensuring subject safety. These safety assessments will continue to provide safety data while minimizing burden to subjects and site personnel.
 
To clarify that despite these alternative measures, all adverse events and serious adverse events should be reported as indicated per protocol.
	
VX15-770-124
 
[REDACTED]
 
[REDACTED]
 
[REDACTED]
 
[REDACTED]
 
[REDACTED]
 
[REDACTED]
 
[REDACTED]
 
[REDACTED]

Summary of Changes in Ongoing CF Clinical Studies for Subjects Who Cannot Travel to the Study Site

Protocol Change	Protocol Change	Protocol Change
Addendum Version 1.0, dated 24 April 2020		

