#### Treatment-emergent (TE) Period

For Part A the TE period will include the time period starting from the first dose date of the study drug to the Follow-up Telephone Call, or the last dose date + 28 days for subjects who do not have a Follow-up Telephone Call. The TE period will be used for safety analyses unless specified otherwise.

For the combined Part B and Part A/B Cohort 8 the TE period will include the time period starting from the first dose date of the study drug to the Follow-up Visit, or to the end of study date for subjects who roll over into the Extension Study and for whom the Follow-up Visit is not required. The last dose date + 28 days will be used as the TE period end date for subjects who do not have a Follow-up Visit or an end of study date. The TE period will be used for safety analyses unless specified otherwise.

**Unscheduled visits:** Unscheduled visit measurements will be included in analysis as follows:

- In scheduled visit windows per specified visit windowing rules (Combined Part B and Part A/B Cohort 8 only).
- In the derivation of baseline measurements.
- In the derivation of maximum/minimum on-treatment values and maximum/minimum change from baseline values for safety analyses.
- In individual subject data listings as appropriate.

**Visit windowing rules:** The analysis visit windows for protocol-defined visits are provided in Appendix D. The windows will be applied using the following rules for both scheduled and unscheduled visits. If no measurement is available within a visit window, the assessment will be considered missing for the visit. If there is more than one measurement available within the same visit window, the following rules will be used:

• For all safety parameters, if there are multiple measurements within a visit window, then 1) the record closest to the target day will be used, with the exception of the threshold analysis in which the worst record will be used; 2) if there are multiple records within the same distance of the target day, the latest record will be used; or 3) the Safety Follow-Up (SFU) visit will not be windowed; instead, the nominal visit will be used in relevant

analyses; 4) the Follow-Up OE visit will not be windowed; instead, the nominal visit will be used in relevant analyses.

- For all efficacy parameters, if there are multiple measurements within a visit window, the record at the scheduled visit will be used. Otherwise,

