#### 8.4 Safety Analysis

The overall safety profile of study drug will be assessed in terms of the following safety and tolerability endpoints:

- Adverse events
- Clinical laboratory values (hematology and serum chemistry)
- OEs
- Physical examinations
- Standard 12-lead electrocardiograms
- Vital signs

Safety endpoints will be analyzed based on the Safety Set, separately for Part A and for the combined Part B and Part A/B Cohort 8. Only a descriptive analysis of safety will be performed. Summary tables will be presented by visit for each cohort, and overall. All safety data will be presented in individual subject data listings. No statistical hypothesis testing will be conducted.

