#### 8.4.6 Ophthalmological Examination

The ocular safety profile of ivacaftor will be assessed in terms of the following analyses:

- Incidence of cataracts or lens opacities based on results from dilated slit-lamp examination
- Red reflex

Results of OEs (incidence of cataracts or lens opacities) will be summarized as a categorical variable and results will be presented by visit.

Lens refracting power and red reflex will be listed as appropriate.

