# Appendix D: Analysis Visit Window Mapping Rules for Safety and Efficacy Assessments

**Table 11-4 Analysis Visit Windows for Safety Assessments for Part B** 

Safety Assessment	Visit a	Target Study Day	Analysis Visit Window (in study days)
Serum Chemistry	Baseline	1	≤1
	Week 2	14	[2,35]
	Week 8	56	[36,70]
	Week 12	84	[71,105]
	Week 18	126	[106,147]
	Week 24	168	[148, Date of Week 24 Visit]
	Follow-up Visit	NA	Use nominal visit
LFTs	Baseline	1	≤1
	Week 2	14	[2,21]
	Week 4	28	[22,42]
	Week 8	56	[43,70]
	Week 12	84	[71,105]
	Week 18	126	[106,147]
	Week 24	168	[148, Date of Week 24 Visit]
	Follow-up Visit	NA	Use nominal visit
Hematology	Baseline	1	≤1
	Week 4	28	[2,42]
	Week 8	56	[43,70]
	Week 12	84	[71,105]
	Week 18	126	[106,147]
	Week 24	168	[148, Date of Week 24 Visit]
	Follow-up Visit	NA	Use nominal visit
Standard 12-Lead ECG	Baseline	1	≤1
	Week 4	28	[2,56]
	Week 12	84	[57,126]
	Week 24	168	[127, Date of Week 24 Visit]
Vital Signs	Baseline	1	≤1

	Week 2	14	[2,21]
	Week 4	28	[22,42]
	Week 8	56	[43,70]
	Week 12	84	[71,105]
	Week 18	126	[106,147]
	Week 24	168	[148, Date of Week 24 Visit]
	Follow-up Visit	NA	Use nominal visit
Ophthalmologic Exam	Baseline	1	≤1
	Week 12	84	[2,126]
	Week 24	168	[127, Date of Week 24 Visit]
	Follow-up OE visit	NA	Use nominal visit

When a subject is lost to follow up and last dose date is unknown, impute last dose date of all study drugs as last on-treatment visit date.

<sup>aVisit name is used to report data in tables, listings and figures.

Table 11-5 Analysis Visit Windows for Efficacy Assessments for Part B

Safety Assessment	Visit a	Target Study Day	Analysis Visit Window (in study days)
	Follow-up Visit	NA	Use nominal visit
weat Chloride	Baseline	1	≤1
	Week 2	14	[2,49]
	Week 12	84	[50,126]
	Week 24	168	[127, Date of Week 24 Visit]

When a subject is lost to follow up and last dose date is unknown, impute last dose date of all study drugs as last on-treatment visit date.

aVisit name is used to report data in tables, listings and figures.

Table 11-6 Analysis Visit Windows for Safety Assessments for Part A/B Cohort 8

Safety Assessment	Visit a	Target Study Day	Analysis Visit Window (in study days)	
Serum Chemistry	Baseline	1	≤1	
	Day 4	4	[2,9]	
	Day 15	15	[10,21]	
	Week 4	28	[22,42]	
	Week 8	56	[43,70]	
	Week 12	84	[71,105]	
	Week 18	126	[106,147]	
	Week 24	168	[148, Date of Week 24 Visit]	
	Follow-up Visit	NA	Use nominal visit	
Hematology	Baseline	1	≤1	

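### In Part B and Cohort 8 the only dedicated lens-opacity/cataract table is by visit, and its window rules can leave out a positive eye examination that a subject-level row would count

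*SAP*

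**What the plan says.** SAP 8.4.6 plans one summary of lens findings: "Results of OEs (incidence of cataracts or lens opacities) will be summarized as a categorical variable and results will be presented by visit". SAP 8.4 sets the general layout: "Summary tables will be presented by visit for each cohort, and overall". Neither section plans a count of subjects with a new finding at any time after baseline. Protocol 13.5.5.6 planned the Part B summary by dose level and the Cohort 8 summary by visit.

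SAP 8.1 puts scheduled and unscheduled records into visit windows for Part B and Cohort 8. For several safety records in one window the rule is "the record closest to the target day will be used, with the exception of the threshold analysis", where the worst record applies. Ties go to the latest record. No section defines a threshold analysis or connects one to OEs. The Follow-up OE is not windowed and keeps its nominal visit.

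Appendix D gives the same OE windows for Part B (safety Table 11-4) and Cohort 8 (Table 11-6). Week 12 has target Day 84 and runs from Day 2 to Day 126. Week 24 has target Day 168 and its window is "127, Date of Week 24 Visit".

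Two protocol provisions can place an OE after the Week 24 Visit.
- COVID-19 Addendum Version 3.0, for assessments missed because of COVID-19: "The unscheduled visit(s) may be conducted at any time during the study (including after the protocol defined last study visit").
- Protocol 12.6.5 on repeats: "If an adequate slit-lamp examination cannot be conducted at any visit where it is required in Part B" (Cohort 8 is named as well), "the subject will continue receiving study drug until an adequate repeat examination is completed (within 4 weeks of the study visit").

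**The concern.** OEs are a named component of the primary safety endpoint in both parts. Choosing the record nearest the target day suits a quantity that is measured repeatedly. It does not suit the incidence of a new finding, where one positive examination is the event and a clean examination some weeks earlier says nothing against it. For liver tests and QTc (SAP 8.4.2 and 8.4.3) the SAP adds maximum on-treatment summaries to the by-visit ones. OEs have no counterpart.

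At stake is whether the one table dedicated to lens findings agrees with the other outputs. With planned cohorts of 5 or 6 subjects, a single record decides whether a row shows a case.

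**Working it through.** **Inputs.** Target Days 84 and 168 and the window limits come from SAP Appendix D. The visit tolerance of ±5 days comes from Protocol Tables 3-2 and 3-4. The selection rule is in SAP 8.1. Minimum numbers come from SAP 6.2: 5 per Part B cohort, 15 in Part B and 6 in Cohort 8, so the overall column has at least 15 + 6 = 21.

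**1. The plan's own window limit.** The midpoint of the two targets is (84 + 168)/2 = 126, which reproduces the upper end of the Week 12 window.

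**2. Displacement inside the Week 12 window.**
- A scheduled Week 12 OE falls on Days 84 ± 5 = 79-89, at most 5 days from target.
- An OE on Day 90 is 90 − 84 = 6 days away, and one on Day 126 is 126 − 84 = 42 days away. Every OE on Days 90-126 is therefore further from target than any scheduled Week 12 OE.
- Number of days: 126 − 90 + 1 = 37. This is the minimum over all scheduled days (Day 79 or Day 89). A clean OE exactly on Day 84 displaces a positive on Days 85-126, which is 42 days.

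**3. Which examinations can be displaced.**
- An ETT OE is not required within 12 weeks of the last OE (Protocol 12.6.5). After a Week 12 OE it becomes required from Day 79 + 84 = 163 to Day 89 + 84 = 173, beyond Day 126. A required ETT OE is not displaced.
- The 4-week repeat follows an inadequate Week 12 OE, so there is normally no clean adequate result to displace it.
- What remains is an unscheduled or otherwise non-required OE.

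**4. After the Week 24 Visit.** That visit falls on Days 168 ± 5 = 163-173, and the window closes on its actual date. An OE recorded later in this study, and not the nominal Follow-up OE, matches no row. A COVID-19 deferred OE is the clearest route. Addendum Version 1.0 says "Safety assessments, as indicated per protocol, may be performed by qualified personnel conducting the in-home visits", and its list does not name OEs. A 4-week repeat would fall between Day 163 + 1 = 164 and Day 173 + 28 = 201.

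**5. No Week 24 Visit.** The Week 24 window then has no stated end. An OE on Days 127-162 (162 − 127 + 1 = 36 days) is not excluded by any rule.

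**6. Effect on the table if one positive OE is displaced** and the Follow-up OE row does not recover it. Intervals are exact (Clopper-Pearson) 95%. For 0/n the upper limit is 1 − 0.025^(1/n). For 1/n the lower limit is 1 − 0.975^(1/n), and the upper limit is the 0.975 quantile of Beta(2, n − 1).

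| Column | All OEs counted | As written |
|---|---|---|
| Part B cohort, n = 5 | 1/5 = 20.0% (0.5-71.6) | 0/5 (0-52.2) |
| Cohort 8, n = 6 | 1/6 = 16.7% (0.4-64.1) | 0/6 (0-45.9) |
| Overall, n = 21 | 1/21 = 4.8% (0.1-23.8) | 0/21 (0-16.1) |

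**The case against.** **The case is normally reported elsewhere.** A new opacity requires dosing to stop (Protocol 10.4 and 12.6.5), and discontinuation is among the criteria for clinical significance in Protocol 14.1.1.2. The case would then appear in the TEAE and treatment-discontinuation tables (SAP 8.4.1) and in the listings (SAP 8.4). This stands and limits the consequence. It is not a complete safeguard, because the investigator judges clinical significance.

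**The same table has a Follow-up OE row.** A subject who stops early is due a Follow-up OE at 24 weeks (Part B) or 12 weeks (Cohort 8), and a persisting opacity would show there. This also stands. The zero in the table therefore depends on that OE being waived (Extension entry within the stated period, or commercial ivacaftor), missed, or no longer positive.

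**Nothing scheduled falls on Days 90-126.** Correct. Displacement needs an extra examination, and its frequency is unknown.

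**The Week 24 repeat is an uncertain route.** The repeat clause assumes continued dosing, yet at Week 24 drug is dispensed only to subjects entering the Extension treatment arm (footnote r of Protocol Tables 3-2 and 3-4). For those subjects the documents do not say which study records a late repeat, so no loss can be claimed. The COVID-19 route is explicit, but nothing shows that any OE was actually deferred.

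**The study is descriptive and the intervals overlap widely.** True, and no conclusion is shown to change.

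**Conclusion.** The point holds as a minor one. As written, the only dedicated lens table is by visit. A clean scheduled Week 12 OE always displaces a positive unscheduled or non-required OE on Days 90-126. An OE recorded in this study after the Week 24 Visit date, other than the Follow-up OE, has no analysis visit. The effect is conditional on such an examination occurring and, for the displaced case, on the Follow-up OE not showing the finding. It is usually a mismatch between outputs and not a lost case. Part A is unaffected, since windowing does not apply there.

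A reader might infer three stronger things that the documents do not support:
- That every OE after Week 24 is dropped. The Follow-up OE keeps its own row.
- That all 73 days between the scheduled examinations (Days 90-162) are lost. Only the first 37 are. The other 36 are a wording gap for subjects with no Week 24 Visit, and the natural reading places those OEs at Week 24.
- That a cataract would vanish from the report. The adverse-event tables and listings would normally show it.

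**What to change.** 1. **SAP 8.4.6.** Add a subject-level row, by cohort and overall: new lens opacity or cataract, absent at the baseline OE, at any post-baseline OE recorded in this study. Count scheduled, repeat, unscheduled, ETT and Follow-up OEs. Footnote any finding that a later adequate examination does not confirm.
2. **SAP 8.1.** For OEs, use the worst record within a window.
3. **Appendix D, Part B and Cohort 8.** Do not move post-treatment OEs into the Week 24 row. Count OEs after the Week 24 Visit in the subject-level row and flag them in the listing. For a subject with no Week 24 Visit, close the window at a stated day, for example the latest allowed Week 24 day (168 + 5 = Day 173), with later OEs counted in the subject-level row only.

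The cost is SAP wording and minor programming on records already held in this study. No examination or visit is added. The downside is that a suspected opacity that is later refuted is counted, with its footnote.

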Adverse events	Continuous from signing ICF through the ETT (if required) and Follow-up Visit (see Section 14.1.1.3)		Ocular adverse events only
Medications and procedures review	Continuous from 28 days before the Screening Visit through the ETT and Follow-up Visit (if required; see Section 10.3.1)		

ECG: electrocardiogram; ETT: Early Termination of Treatment; ICF: informed consent form; OE: ophthalmologic examination; PK: pharmacokinetic.

Table 3-4 Study VX15-770-124: Part A/B Cohort 8 (Screening, Treatment, Early Termination of Treatment, and Follow-up Periods)

Event/Assessment	Screening Period	Treatment Period (Day 1 to Week 24)							Early Termination of Treatment Visit ^a	Follow-up Visit ^b	Follow-up Ophthalmologic Examination ^c
	Day -28 to Day -14	Day 1	Day 4	Day 15 (± 1 Day)	Day 17 (± 1 Day)	Week 4 (± 5 Days)	Week 8 (± 5 Days)	Weeks 12, 18, and 24 (± 5 Days)	As Soon as Possible After the Last Dose of Study Drug	4 Weeks (± 7 Days) After Last Dose of Study Drug	12 Weeks (± 14 Days) After Last Dose of Study Drug
Informed consent ^d	X										
Inclusion/exclusion criteria review	X	X									
Clinic visit/ Assessment contact	X	X	X	X		X	X	X	X	X	
Telephone contact		pm			X						
Demographics	X										
Medical history	X										
██████████ weight ^e	X	X	X	X		X	X	X	X	X	
Physical examination ^f	X	X	X	X		X	X	X	X	X	
Vital signs ^g	X	X	X	X		X	X	X	X	X	
12-lead ECGs ^h	X		X			X		X	X		
Ophthalmologic examinations ⁱ	X							X ^j	X		X
Serum chemistry ^k	X	X	X	X		X	X	X	X	X	
Hematology ^k	X			X		X		X	X	X	
PK blood collection ^l			X ^m	X		X	X ^l	X	X ⁿ		
Sweat chloride test ^o	X	X		X		X	X	X	X		
Study drug administration ^q		X	X	X		X	X	X			

-
- ^a Subjects who prematurely discontinue treatment before their last scheduled dose will be required to complete the ETT Visit as soon as possible after the last dose of study drug and the Follow-up Visit. All subjects who prematurely discontinue from study drug treatment in Part A/B Cohort 8 will be eligible to enroll in an observational arm of the Extension Study.
- ^b The Follow-up Visit is not required if the subject completes the Part A/B Cohort 8 treatment period and enrolls in the treatment arm of the Extension Study. For all other subjects, the Follow-up Visit is not required if the ETT Visit occurs 3 weeks or later after the last dose of study drug (ivacaftor) or in the event that the subject initiates treatment with commercially available ivacaftor within 3 weeks of the final scheduled treatment visit or ETT Visit.

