- ^k To minimize the volume of blood drawn on Day 1, clinical laboratory assessments will be determined from a single blood draw taken during the Screening Period Day -28 to Day -14. The results must be received and reviewed before the first dose of study drug. All blood samples will be collected while subjects are in a seated or supine position.
- ^l PK samples will be collected before the morning dose and between 2 to 4 hours and between 6 to 8 hours after the morning dose on Day 4 and the Week 8 Visit. PK samples will be collected before the morning dose on Day 15, and on the Week 4, 12, 18, and 24 Visits.
- ^m If all PK samples collected on Day 4 are missing or cannot be analyzed, PK samples collected on Day 15 will be used to assess whether the initial dose should be adjusted at the Week 4 Visit.
- ⁿ Assessment will be performed only if within 3 days of last dose of study drug.
- ^o At Screening a sweat chloride test must be performed if the sweat chloride value is not available in the subject's medical records and the value is needed to establish eligibility. For subjects with sweat chloride values documented in their medical records and for whom it is not needed to establish eligibility, the sweat chloride test at screening is not required. At the Day 1 Visit, the sweat chloride test must be performed before the morning dose. At the Day 15 and Week 4, 8, 12, 18 and 24 Visits, the sweat chloride test must be performed within a window of ± 2 hours relative to the morning dose of the study drug.
- [REDACTED]

Table 3-4 Study VX15-770-124: Part A/B Cohort 8 (Screening, Treatment, Early Termination of Treatment, and Follow-up Periods)

Event/Assessment	Screening Period	Treatment Period (Day 1 to Week 24)							Early Termination of Treatment Visit ^a	Follow-up Visit ^b	Follow-up Ophthalmologic Examination ^c
	Day -28 to Day -14	Day 1	Day 4	Day 15 (± 1 Day)	Day 17 (± 1 Day)	Week 4 (± 5 Days)	Week 8 (± 5 Days)	Weeks 12, 18, and 24 (± 5 Days)	As Soon as Possible After the Last Dose of Study Drug	4 Weeks (± 7 Days) After Last Dose of Study Drug	12 Weeks (± 14 Days) After Last Dose of Study Drug
In-clinic observation for 4 hours after administration of the first dose of study drug		X									
Study drug count		X		X		X	X	X	X		
Study drug dispensing		X		X		X	X	X ^r			
Adverse events	Continuous from signing of ICF through ETT and Follow-up Visit (if required; see Section 14.1.1.3)									Ocular adverse events only	

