12.4.1 Sweat Chloride

The sweat chloride test is a standard diagnostic tool for CF, serving as a biomarker of CFTR activity. Collection of sweat samples will be performed at qualified study sites using an approved Macroduct® (Wescor, Logan, UT) collection device. Sweat samples will be sent to a central laboratory for testing and interpretation of results. Individual sweat test results will not be disclosed to the study sites. Specific instructions for collection, handling, processing, and shipping of sweat chloride samples to the central laboratory will be provided separately.

Sweat collection will be completed at visits as indicated in Part A [Table 3-1](#), Part B [Table 3-2](#), and Part A/B Cohort 8 [Table 16-1](#). In Part B and in Part A/B Cohort 8, the sweat chloride test at the Day 1 Visit must be performed before the morning dose. At subsequent visits, the sweat chloride test must be performed within a window of ± 2 hours relative to the morning dose of the study drug. Change from baseline in sweat chloride will be analyzed as a secondary endpoint of Part B and Part A/B Cohort 8 in this study

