  - if there are no measurements at the scheduled visit, then the record closest to the target day will be used;
  - if there are multiple records with the same distance to the target day, the latest record will be used.
  - assessments at the ETT visit will follow the windowing rules for regular visits.
  - assessments at SFU visit will follow the windowing rules for regular visits if they fall
    within the upper boundary of the window for the last scheduled visit; it will remain as
    the SFU if it goes beyond the upper boundary of the window for the last scheduled
    visit.

Incomplete/missing data will not be imputed, unless specified otherwise.

**Outliers:** No formal statistical analyses will be performed to detect or remedy the presence of statistical outliers, unless specified otherwise.

**Multiplicity:** No multiplicity adjustment will be performed for hypothesis testing.

All analyses will be done separately for Part A, and combined Part B and Part A/B Cohort 8, as applicable. Unless otherwise specified, summary tables will be presented by cohort and overall.

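### Cohort 8 sweat chloride from a late early-termination visit can be reported as an on-treatment visit result, because the SAP windows it by study day with no limit on time since last dose

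*SAP*

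**What the plan says.** **Windowing.** Under the visit windowing rules in SAP Section 8.1, efficacy "assessments at the ETT visit will follow the windowing rules for regular visits". The Cohort 8 sweat chloride windows (SAP Table 12-7) are ranges of study days. When a window holds several measurements, "the record at the scheduled visit will be used"; the closest record to the target day is used only if there is none from the scheduled visit.

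**Collection at ETT.** The sweat chloride row of Protocol Table 3-4 is marked at the ETT visit and blank at the Follow-up Visit. The Cohort 8 schedule in SAP Appendix A agrees.

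**Timing of ETT.** Subjects who stop early are "required to complete the ETT Visit as soon as possible after the last dose of study drug and the Follow-up Visit" (Table 3-4, footnote a). No number of days is set. Footnote b foresees a long gap: "the Follow-up Visit is not required if the ETT Visit occurs 3 weeks or later after the last dose of study drug".

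**Closeness to dosing.** For the PK sample at ETT, footnote n states "Assessment will be performed only if within 3 days of last dose of study drug". For sweat chloride, footnote o reads "At the Day 15 and Week 4, 8, 12, 18 and 24 Visits, the sweat chloride test must be performed within a window" and does not name ETT. Protocol Section 12.4.1 is broader: "At subsequent visits, the sweat chloride test must be performed within a window of ± 2 hours relative to the morning dose".

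**Exclusions.** SAP Section 8.3.2 drops sweat chloride results only for low sample volume or a concentration above 160 mmol/L. The treatment-emergent period in SAP Section 8.1 is defined for safety analyses.

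**The concern.** The secondary objective for Cohort 8 is the pharmacodynamics of ivacaftor treatment (Protocol Section 7.2.2, SAP Section 4.2), and change in sweat chloride is the one secondary endpoint visible for it. Protocol Section 12.4.1 ties post-baseline sweat tests closely to a dose. That is a collection rule, however, and nothing in the SAP carries it into the analysis.

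A value taken weeks after the last dose can therefore be reported under a scheduled visit name with nothing to mark it as untreated. Such a value pulls the mean change toward zero. With only 6 to about 10 infants, one value carries real weight in a visit mean. SAP Section 8.3 presents results for each cohort as well as overall, so pooling with Part B does not protect the Cohort 8 figures.

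**Working it through.** **1. Reading the windows.** The plan states no power or precision figure for sweat chloride, so there is none to reproduce. As a check on the windows, take midpoints of consecutive target days (15, 28, 56, 84, 126, 168), rounded down: (15+28)/2 → 21; (28+56)/2 = 42; (56+84)/2 = 70; (84+126)/2 = 105; (126+168)/2 = 147. All five match the upper bounds in SAP Table 12-7, which confirms that study day alone defines the windows.

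**2. How long off drug an ETT value could be.** Suppose the last dose fell on the target day of the previous scheduled visit and the next visit was not attended.

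| Window | Study days | Last dose (day) | Days off drug if ETT falls in the window |
|---|---|---|---|
| Day 15 | 2–21 | 4 | 0 to 17 |
| Week 4 | 22–42 | 15 | 7 to 27 |
| Week 8 | 43–70 | 28 | 15 to 42 |
| Week 12 | 71–105 | 56 | 15 to 49 |
| Week 18 | 106–147 | 84 | 22 to 63 |

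A later last dose shortens these gaps. The Week 24 window is left out because it ends on the date of the Week 24 visit, which a discontinuer may not have. The SAP does not say what then happens to an ETT value after Day 147.

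**3. Shift in a visit mean.** Let E be the on-drug effect, n the number of values in the window including k off-drug ones, and r the share of effect retained off drug.

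Mean = E × [1 − k(1 − r)/n], so the shift is E × k(1 − r)/n.

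- E: 30 to 40 mmol/L reduction, the range Protocol Section 5.3 gives for the 25 mg dose in Study 101. It is an illustration, not an infant estimate.
- n: 6 to 10 (SAP Section 6.2).
- k and r: not in the documents; assumed k = 1 and r = 0 or 0.5.

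| n | r | Shift (mmol/L) | Share of effect |
|---|---|---|---|
| 6 | 0 | 30/6 = 5.0 to 40/6 = 6.7 | 16.7% |
| 6 | 0.5 | 2.5 to 3.3 | 8.3% |
| 10 | 0 | 30/10 = 3.0 to 40/10 = 4.0 | 10% |
| 10 | 0.5 | 1.5 to 2.0 | 5% |

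Protocol Section 9.3.3 notes that sweat chloride rises over the first 6 months of life, so an off-drug value could exceed baseline. No rate is given, and this is not counted here.

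**4. The overall column.** Part B tests sweat chloride at Weeks 2, 12 and 24 only (Table 3-2). At Weeks 4, 8 and 18 the overall column therefore holds Cohort 8 alone and the shares above apply. At Week 12, with the minimum of 15 in Part B plus 6 to 10, one fully off-drug value dilutes the mean by 1/21 = 4.8% to 1/25 = 4.0%.

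**5. Spread.** Assume E = 35 and on-drug SD s (not in the documents), with five on-drug values and one zero-change value. The new variance is [4s² + (5/6)(35²)]/5.

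- s = 10: (400 + 1020.8)/5 = 284.2, SD 16.9. The 95% CI half-width goes from 2.776 × 10/√5 = 12.4 (without the value) to 2.571 × 16.9/√6 = 17.7 (with it).
- s = 20: (1600 + 1020.8)/5 = 524.2, SD 22.9. The half-width goes from 24.8 to 24.0.

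The SD rises in both cases, but the interval does not always widen.

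**6. Chance that the situation arises.** P(at least one discontinuer) = 1 − (1 − d)ⁿ. For assumed d of 5%, 10% and 20% this is 0.27, 0.47 and 0.74 at n=6, and 0.40, 0.65 and 0.89 at n=10. These are upper limits for the problem, because a discontinuer need not have a late ETT or an otherwise empty window.

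**The case against.** **Precedence limits the reach.** A scheduled-visit record displaces the ETT value within its window, so an ETT soon after an attended visit usually changes nothing. A reader might infer that off-drug values can spread across the results from Week 4 to Week 24. The documents do not support that: each discontinuer has one ETT visit, so at most one visit mean is touched, and mapping to Week 24 is undefined rather than shown to be affected. This part of the objection stands in full.

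**The size is conditional.** It needs a discontinuation, a late ETT despite the instruction to hold it promptly, no scheduled record in the window, and loss of effect. The three-week clause is a contingency for waiving the Follow-up Visit, not expected timing. This also stands.

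**The PK limit proves little.** A reader might take the 3-day limit at ETT as the protocol's own definition of being on drug. Footnote n gives no reason for it. Infant blood volume is a stated concern elsewhere and could explain it. In Part A the ETT visit falls within 5 days of the last dose, and no limit is visible for the Part B ETT sample. The limit cannot be read as a sweat chloride washout time.

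**Keeping the value may be deliberate.** The full analysis set includes every eligible dosed subject, missing data are not imputed, and using the ETT value retains discontinuers who would otherwise drop out of the summary. No estimand is stated either way. But no treatment-policy aim is stated, and no sweat chloride is scheduled after ETT. A discontinuer would contribute one off-drug value to one window and then go missing, which is not a coherent treatment-policy summary.

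**Little depends on the mean.** The analysis is descriptive and unpowered, Cohort 8 dose adjustment uses PK, and individual data are listed. This limits the consequence but does not correct the visit label.

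**Conclusion.** The gap is real and confined to Cohort 8 and any overall column that includes it; the visible Part B ETT schedule (Protocol Table 3-3) has no sweat chloride test. As written, the rule can report an untreated value as an on-treatment visit result, contrary to the stated objective.

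For one discontinuer, the effect is limited to one visit mean. The 10% to 17% shift rests on full return to baseline and an adult effect size, so it should be read as an illustrative worst case and not as an expected bias. With half the effect retained it is 5% to 8%. How often this would occur cannot be estimated from the documents. No type I error or power is involved; the consequence is a biased descriptive mean and a mislabelled value. The change is worth making because it is small.

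**What to change.** - In the efficacy windowing rules of SAP Section 8.1, state that an ETT sweat chloride value enters the by-visit summaries only if collected within a pre-specified number of days of the last dose. The 3-day limit used for the ETT PK sample is one available choice; it is not a documented pharmacodynamic washout, and the SAP should give its reason for whatever limit it adopts.
- List later values as off-treatment, with days since last dose, and show the affected visit with and without them.
- In SAP Table 12-7, define the upper bound of the Week 24 window for subjects with no Week 24 visit.

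No new data are needed. The last dose date is already used for exposure (SAP Section 8.2.4), and Appendix D imputes it when unknown for subjects lost to follow-up. The cost is a few sentences and one supportive summary. The downside is that a late ETT value leaves the main by-visit n, though it stays in the listing and the supportive summary. If the database is already locked, SAP Section 3 provides for documenting the change in the clinical study report.
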